#### 2.3.1 Randomization

There will be no randomization to dose/volume of PC-1005 in this open-label, sequential dose/volume escalation trial. However, upon enrollment a participant will be assigned to a randomly selected sequence of pharmacokinetic sampling times for administration of flexible sigmoidoscopy biopsy procedures. Each participant will have a total of 5 flexible sigmoidoscopies:

- at baseline (1 set of biopsies);
- within 24 hours of each of the three dose/volume gel applications (one of the following randomly selected times: 0.5-1 hour, 1.5-3 hours, 3.5-5 hours, or 24 hours after gel administration for each dose/volume of gel) (total of 3 sets of biopsies), and
- 48 hours after one of the three dose/volume gel applications (to be determined at random) (1 set of biopsies).

The sampling schedule for a participant will be preassigned at the enrollment visit.

The determination of the sample schedule will achieve the following characteristics:

- All 12 participants will have flexible sigmoidoscopy at enrollment.
- For the 4 mL, 16 mL, and 32 mL dose/volumes, participants will be randomly assigned 1:1:1:1 to one of the following 4 time-frames to provide samples of rectal tissue, rectal fluid, vaginal fluid (if applicable), and effluent from rectal lavage: 0.5-1 hour, 1.5-3 hours, 3.5-5 hours, and 24 hours following PC-1005 gel application.

- There will be 3 sets of biopsies available at each time-frame (0.5-1 hour, 1.5-3 hours, 3.5-5 hours, and 24 hours following PC-1005 gel application) for each dose/volume (4 mL, 16 mL, and 32 mL).
- Across the three dose/volumes (4 mL, 16 mL, and 32 mL), participants will be randomly assigned 1:1:1 to provide samples of blood, rectal tissue, rectal fluid, vaginal fluid (if applicable), and effluent from rectal lavage 48 hours following PC- 1005 gel application for one of the three dose/volumes.
- There will be 4 sets of biopsies available at 48 hours following PC-1005 gel application for each dose/volume (4 mL, 16 mL, and 32 mL).
- Randomizations will be stratified by gender so as to incorporate 1-2 participants of each gender at each of four time-frames between 0.5 and 24 hours, and to incorporate 2 participants of each gender at 48 hours for each dose/volume.

#### 2.3.2 Blinding

There is no blinding in this open-label study.

# 2.3.3 Sample Size and Power

The study is designed for a total accrual of twelve (12) participants, which gives sufficient power for the detection of events (adverse events or detection of drug) as described in the protocol. Descriptive safety analyses and pharmacokinetic analyses are planned with no formal statistical testing.

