7.4 Follow-up Visits

7.4.1 Dosing – Visits 3, 5, and 7

The first dosing on Visit 3 should occur approximately 14 days after the Enrollment Visit.

After a two-to-six-week washout period (to accommodate scheduling around the menstrual cycles of female participants) following each dosing visit, participants will return to the clinic for assessment. If no adverse events (AEs) that preclude continuation to the next dose are identified (based on product hold criteria in Section 9 and discretion of the loR/designee), participants will receive the next scheduled dose of the study gel. Please see the SSP Manual for additional information.

All participants will undergo PK and PD assessments within 24 hours after each gel administration. Participants will be randomized 1:1:1:1 to one of the following 4 time frames to provide samples of rectal tissue, rectal fluid, vaginal fluid (if applicable), and effluent from rectal lavage: 0.5-1 hour, 1.5-3 hours, 3.5-5 hours, and 24 hours following PC-1005 gel application. This time frame will remain consistent across gel volumes.. Procedures for the day of dosing are listed in

Table 13 below.

Table 13: Dosing Procedures

able 1	3: Dosing Procedures	ing Dunnadanan Maita O. F. and 7	
	Dosing Procedures – Visits 3 , 5, and 7 Component Procedures		
	Component		
Admi	inistrative and Regulatory	Noview aparte locater information	
		Provide reimbursement	
		Schedule next visit/contact	
Е	Behavioral/Counseling	Protocol counseling	
		Behavioral assessment	
		Review/update medical history	
		 Perform targeted physical examination* 	
		Perform male genital examination*	
		Perform pelvic examination*	
	Clinical	Perform rectal examination	
		Review/update concomitant medications	
		Treat or prescribe treatment for RTI/UTI, or STIs*	
		Disclose available test results	
		Record/update AEs	
	Pharyngeal	NAAT for GC/CT*	
		NAAT for GC/CT*	
	Urine	Urine dipstick/culture*	
		Qualitative hCG ♀	
		CBC with differential and platelets*	
حَ	Blood	Chemistries (Creatinine only)	
ato	2.000	Syphilis serology*	
Laboratory		Blood for PK ■ Blood fo	
La	Pelvic	Vaginal fluid for PK△♀	
		NAAT for GC/CT/TV*♀	
		Rectal enema effluent for PD prior to biopsy collection ∴	
	Anorectal	Rectal fluid for PK and PD	
	Allolottal	Rectal tissue for PK, PD, histology, and archive	
		HSV 1/2 detection*	
		NAAT for GC/CT*	
S	tudy Product/Supplies	Administration of study product	
		Offer condoms	

^{*} If indicated. ♀Female participants.

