10 STATISTICAL CONSIDERATIONS

10.1 Overview and General Design

MTN-037 is a phase 1, open label, sequential dose/volume escalation trial designed to characterize the PK and safety profiles of a single dose of PC-1005 (0.002% MIV-150/0.3% zinc acetate [ZA] in 3.0% carrageenan [CG] gel) administered rectally via applicator in the clinic. Twelve HIV-uninfected men and women, 18 years or older will receive a single dose of each dose/volume (4 mL, 16 mL, and 32 mL) in sequential order allowing time for adequate washout before application of the subsequent dose.

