10.5 Randomization Procedures

There will be no randomization to dose/volume of PC-1005 in this open-label, sequential dose/volume escalation trial. However, upon enrollment a participant will be assigned to a randomly selected sequence of pharmacokinetic sampling times for administration of flexible sigmoidoscopy biopsy procedures.

Each participant will have a total of 5 flexible sigmoidoscopies:

- at baseline (1 set of biopsies);
- within 24 hours of each of the three dose/volume gel applications (one of the following randomly selected times: 0.5-1 hour, 1.5-3 hours, 3.5-5 hours, or 24 hours after gel administration for each dose/volume of gel) (total of 3 sets of biopsies), and
- 48 hours after one of the three dose/volume gel applications (to be determined at random) (1 set of biopsies).

The sampling schedule for a participant will be preassigned at the enrollment visit.

The determination of the sample schedule will achieve the following characteristics:

- All 12 participants will have flexible sigmoidoscopy at enrollment.
- For the 4 mL, 16 mL, and 32 mL dose/volumes, participants will be randomly assigned 1:1:1:1 to one of the following 4 time frames to provide samples of rectal tissue, rectal fluid, vaginal fluid (if applicable), and effluent from rectal lavage: 0.5-1 hour, 1.5-3 hours, 3.5-5 hours, and 24 hours following PC-1005 gel application.
- There will be 3 sets of biopsies available at each time frame (0.5-1 hour, 1.5-3 hours, 3.5-5 hours, and 24 hours following PC-1005 gel application) for each dose/volume (4 mL, 16 mL, and 32 mL).
- Across the three dose/volumes (4 mL, 16 mL, and 32 mL), participants will be randomly assigned 1:1:1 to provide samples of blood, rectal tissue, rectal fluid, vaginal fluid (if applicable), and effluent from rectal lavage48 hours following PC-1005 gel application for one of the three dose/volumes.
- There will be 4 sets of biopsies available at 48 hours following PC-1005 gel application for each dose/volume (4 mL, 16 mL, and 32 mL).
- Randomizations will be stratified by gender so as to incorporate 1-2 participants of each gender at each of four time frames between 0.5 and 24 hours, and to incorporate 2 participants of each gender at 48 hours for each dose/volume.

The randomization scheme will be generated and maintained by the MTN SDMC.

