10.7.2 Primary Analysis

When the use of descriptive statistics to assess group characteristics or differences is required, the following methods will be used: for categorical variables, the number and percent in each category; for continuous variables, the mean, median, standard deviation, quartiles and range (minimum, maximum). Within-treatment group assessment of the change from the baseline measurement to a follow-up measurement will be analyzed using McNemar's test (for categorical response variables) or the paired t-test or Wilcoxon signed-ranks test (for continuous variables).

Safety Endpoints

All visits in which a participant has been exposed to the study product will be included in the primary analyses of safety. Secondary intent to treat analyses may also be performed. The number and the percentages of participants experiencing each safety endpoint (see Section 10.2) will be tabulated by dose/volume of gel. Each participant will contribute once in each category (i.e., only for highest severity AE for each participant) for the calculation of event rates for each dose/volume of gel.

To assess the overall tolerability of the 3 dose/volumes of gel, participants in each dose/volume may be compared for characteristics including safety events and laboratory measurements using descriptive statistics. Due to the small sample size, formal comparisons will not be done.

Pharmacokinetic/Pharmacodynamic Analysis

We will use descriptive statistics such as the mean and median and corresponding 95% confidence intervals to describe the MIV-150 concentrations in all biological matrices assessed at all scheduled time points. For each dose/volume of gel, the 0.5 to 48 hour time points will be used to describe the concentrations beginning soon after a gel dose through time to peak concentrations through initial elimination among different matrices.

Concentrations will be compared among and between volume arms using paired analyses.

Ex vivo HIV explant data will use cumulative p24 to compare baseline with study product. Concentration-response relationships will also be explored using appropriate linear and non-linear models. Rectal lavage fluid will be assessed for anti-HIV activity and the percent inhibition will be correlated to MIV-150 concentrations.

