# **Secondary Objectives:**

#### **Acceptability**

To compare the acceptability of PC-1005 gel formulation across the three doses when administered rectally

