#### 10. SECONDARY ANALYSES

# 10.1 Acceptability Analyses

Enrolled participants are administered web-based self-interviews (WSI) at Enrollment (Visit 2) and at the three dosing visits (Visits 3, 5, and 7). The WSI at dosing visits explore reactions to product, with an emphasis on identification of product attributes likely to challenge and/or facilitate future sustained use when applied rectally by participants.

To address the secondary endpoints of participant self-report of comfort with gel application, liking the product across doses, and perceived side-effects, responses to WSI questions in section B (Rectal Gel Acceptability) and section C (Experiences Using the Product) of the dosing visits (Visits 3, 5, and 7) will be summarized in a table by dose/volume.

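### The protocol commits to paired comparison of MIV-150 concentrations between gel volumes, but the SAP plans only separate per-volume summaries and does not acknowledge the change

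*SAP*

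**What the plan says.** **Design.** Protocol 10.1: "Twelve HIV-uninfected men and women, 18 years or older will receive a single dose of each dose/volume", in the fixed order 4, 16, 32 mL. Each participant can therefore serve as their own control.

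**Protocol on concentrations.** Section 10.7.2, under the pharmacokinetic/pharmacodynamic analysis: "Concentrations will be compared among and between volume arms using paired analyses". The same section also says "Due to the small sample size, formal comparisons will not be done", but that sentence closes the paragraphs on safety endpoints and tolerability. It does not qualify the PK text.

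**SAP on concentrations.** Section 2.3.3: "Descriptive safety analyses and pharmacokinetic analyses are planned with no formal statistical testing". For plasma, section 9.2 lists concentration tables, individual and mean/median plots with 95% CIs, parameter listings and parameter summaries, each organised by volume. Rectal fluid and tissue get per-volume tables, plots and parameters calculated from the mean or median profile. Section 10.2 repeats this for vaginal fluid. The paired t-test, signed-rank test and McNemar's test in SAP 5 are for change from baseline within a volume group.

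**Tissue time frame.** Protocol 7.4.1: "This time frame will remain consistent across gel volumes". Protocol 10.5 speaks of "a randomly selected sequence of pharmacokinetic sampling times" and describes the random time as applying to each volume. SAP 2.3.1 carries the section 10.5 wording.

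**Acceptability.** The objective in SAP 2.1 is "To compare the acceptability of PC-1005 gel formulation across the three doses when administered rectally". SAP 10.1 says the relevant questionnaire responses "will be summarized in a table by dose/volume".

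**The concern.** How exposure changes as the volume rises is a natural question for a volume-escalation study, and the protocol says how it will be answered: volume against volume, within participant. The SAP contains no such contrast for any matrix and gives no reason for leaving it out. A reader of the final report would see three per-volume summaries and would have to judge the volume effect by eye, from intervals that ignore the fact that the same people are in each column.

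The answer is not obvious in advance. In the rabbit rectal study (protocol 2.4), raising the dose concentration from 3x to 5x took Day 1 AUC only from about 3.0-fold to 3.5-fold of the 1x value. That was a change in concentration, not volume, but it shows that rectal exposure need not scale simply with dose.

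**Working it through.** **Step 1. Is there a figure to reproduce?** The plan gives none for a between-volume comparison. Protocol Tables 18 and 19 concern safety events in 12 people. They reproduce (for example the 0/12 upper bound is 1 − 0.025^(1/12) = 26.46%, printed as 26.4), but they do not bear on this point.

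**Step 2. Where does pairing exist?**

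| Matrix and time | Participants with values at all three volumes |
|---|---|
| Plasma to 24 h | up to 12 |
| Rectal fluid and tissue, each of four time frames to 24 h | 12/4 = 3, if the time frame is held across volumes as protocol 7.4.1 says |
| Any matrix at 48 h | 0; each participant attends one 48-hour visit, so 12/3 = 4 different people per volume |

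**Step 3. What does pairing change?** With complete data, mean(log x16) − mean(log x4) = mean(log x16 − log x4). The estimated ratio is the same with or without pairing; the interval differs.

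**Step 4. Size for plasma, n = 12.** The log-scale SDs are assumptions: between participants sB, within participants sW.

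- Paired half-width: t(0.975, 11) × √2 × sW/√12
- Half-width ignoring pairing: t(0.975, 22) × √(2(sB² + sW²)/12)

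With sB = 0.6 and sW = 0.4:

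- Paired: 2.201 × 0.1633 = 0.359; exp = 1.43
- Ignoring pairing: 2.074 × √(1.04/12) = 2.074 × 0.2944 = 0.611; exp = 1.84

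| Assumed sB, sW | Implied correlation sB²/(sB² + sW²) | Paired | Pairing ignored |
|---|---|---|---|
| 0.5, 0.5 | 0.50 | ×/÷1.57 | ×/÷1.82 |
| 0.6, 0.4 | 0.69 | ×/÷1.43 | ×/÷1.84 |
| 0.8, 0.3 | 0.88 | ×/÷1.31 | ×/÷2.06 |

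**Step 5. Cross-check with a variability figure from the documents.** Protocol 2.5 gives a Cmax CV of 48.1% in five women dosed vaginally. If that carries over to rectal dosing (an assumption), the log SD is √ln(1 + 0.481²) = 0.456. The n = 12 interval is ×/÷1.47 ignoring pairing. Paired, it is ×/÷1.34 at correlation 0.5, 1.25 at 0.7 and 1.14 at 0.9. Pairing gains precision once the correlation exceeds 1 − (2.074/2.201)² ≈ 0.11.

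**Step 6. Rectal samples at one time frame, n = 3.**

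- SDs 0.6 and 0.4: paired 4.303 × √2 × 0.4/√3 = 1.405, exp = 4.1; pairing ignored 2.776 × √(1.04/3) = 1.635, exp = 5.1.
- SDs 0.5 and 0.5: paired ×/÷5.8, pairing ignored ×/÷5.0, so pairing is worse.
- Break-even correlation is about 0.58.

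Pooling the 12 rectal pairs with time frame as a stratum leaves 12 − 4 = 8 df. With sW = 0.4: 2.306 × 0.1633 = 0.377; exp = 1.46. This assumes one common volume ratio at every time frame.

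**Step 7. Which AUC?** SAP 9.2 runs AUC0-t to the last sample, typically 24 or 48 h. Each participant has a 48 h plasma sample at only one volume, so a within-participant ratio of AUC0-t can set a 48 h area against a 24 h area. AUC0-24 gives a common horizon.

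**The case against.** The strongest reply is that the SAP does little harm. It plans no unpaired contrast, so it produces no wrong interval. With complete data its columns hold the same people, so a ratio read from geometric means would equal the paired one (Step 3). Participant-level listings are kept for each volume, so pairs can be rebuilt. The PK objective is to characterise, not to test proportionality. All of this stands, and it rules out saying that the SAP biases the volume effect or destroys the pairing. It does not supply the comparison that the protocol said would be made, or its interval. The equality also needs complete data: SAP 3.2 drops a participant from any volume not received, and protocol 10.4 allows replacements, so the columns may come to differ in membership.

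Three limits on any paired analysis also stand:

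- Volume order is fixed, so each ratio is volume plus period.
- SAP 9.1 sets values below quantification to zero for descriptive statistics, which leaves a log ratio undefined.
- At 48 h the protocol's unqualified promise cannot be met.

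A reader might take SAP 2.3.3 as authority for dropping the comparison. Ruling out tests does not rule out paired estimates with intervals, and the protocol's own bar on formal comparisons sits under safety.

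**Conclusion.** The mismatch is real and lies in the text of protocol 10.7.2 against SAP 9.2. It is firmest for plasma to 24 h. There, a paired 95% CI would be about ×/÷1.43 against ×/÷1.84 with pairing ignored, or 1.3–1.6 against 1.8–2.1 over the splits tried. These sizes rest on assumed SDs, because the documents report no within-participant correlation.

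Stronger readings that a reader might infer are not supported:

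- **That pairing shrinks the interval from ×/÷5.1 to ×/÷1.43.** That sets three people per volume against 12 pairs, so it changes sample size and pairing together.
- **That every rectal value has a match at another volume.** None does at 48 h, and within one time frame three pairs help only at high correlation.
- **That the acceptability analysis breaks a promise.** Neither document names a paired method for it. A table by volume is a weak descriptive comparison, but it is one.
- **That the oral data make a proportionality model necessary.** Protocol 2.5 is mixed: its text says less than proportional, while Table 8 reports proportionality in two studies. Those doses were 200–1600 mg, against 8 × 73.6 µg ≈ 0.59 mg at 32 mL. A fitted slope is a matter of preference.

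**What to change.** **Plasma (SAP 9.2).** Add within-participant geometric mean ratios 16/4, 32/4 and 32/16 mL for Cmax and AUC0-24, with 95% CIs, as estimates without tests. State how pairs with values below quantification are handled and how many are excluded. State that the fixed order makes each ratio volume plus period.

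**Rectal fluid and tissue.** Show linked individual values matched on time frame up to 24 h. Stratify any ratio pooled over time frames by time frame, and note that it assumes a common ratio. Leave 48 h out of between-volume contrasts.

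**Time frame (SAP 2.3.1).** Confirm that each participant's time frame was held constant across volumes, as protocol 7.4.1 states.

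**Acceptability (SAP 10.1).** Within-participant change in the comfort, liking and side-effect items is a low-cost option.

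If the team prefers not to make the paired comparison, the SAP should say so and give the reason.

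**Cost.** SAP wording and a small amount of code. No new data are needed. SAP 4 already records a December 2018 monitoring review, so the changes are best confined to the SAP.

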### 3. GENERAL DATA ANALYSIS CONSIDERATIONS

#### 3.1 Analysis Set(s)

The analysis set consists of all participants enrolled in the study who are administered PC-1005 at any dosing visit (Visit 3, Visit 5, or Visit 7). All available safety, PK, and acceptability data will be analyzed on this set of participants, as described below.

#### 3.2 Statistical Analysis Issues

For the primary safety analyses, safety endpoints will be classified into groups by dose/volume of gel based on the amount of gel administered at a dosing visit (Visit 3, Visit 5, and Visit 7). If a participant was not administered a particular dose/volume of gel, then the participant will be excluded from analyses describing that particular dose/volume group.

For the primary pharmacokinetics analyses, timing of drug concentration results will be based on the time the specimen was actually taken, and not based on timing group as randomized. Time points may still be grouped into categories based the average or targeted time point for specimen collection. The handling of missing data and concentration data below the limit of quantitation (BLOQ) are described in the section on pharmacokinetic analyses below.

# 4. INTERIM ANALYSIS AND DATA MONITORING COMMITTEE

No interim statistical analysis was planned or performed for the MTN-037 study.

One study monitoring committee (SMC) review was conducted for MTN-037, on December 10, 2018, for which a closed report was produced. Evaluation of safety was based on descriptive tables of adverse events, with no formal statistical testing.

# 5. GENERAL ANALYSIS METHODS

When the use of descriptive statistics to assess dose/volume group characteristics or differences is required, the following methods will be used: for categorical variables, the number and percent in each category; for continuous variables, the mean, median, standard deviation, quartiles, and range (minimum, maximum). Within-treatment group assessment of the change from the baseline measurement to a follow-up measurement will be analyzed using McNemar's test (for categorical response variables) or the paired t-test or Wilcoxon signed-ranks test (for continuous variables).

The following descriptions may be used to distinguish the dose/volume groups: "4 mL Volume", "16mL Volume", and "32 mL Volume".

# 6. TRIAL PARTICIPANT DISPOSITION

Enrollment will take place at two sites: Birmingham and Pittsburgh, USA.

# **6.1 Disposition of Participants**

#### 6.1.1 Screening and Enrollment

Dates of site activation, first enrollment, and last enrollment, as well as the number or participants screened, number and percentage of participants enrolled, and the screening-to-enrollment ratio will be displayed in a table overall and by site.

#### 6.1.2 Retention

A table will display for each visit the number and percentage of participants who are expected, retained, missing, and lost-to-follow-up or terminated with respect to that visit, overall and by site.

#### 6.1.3 Treatment Discontinuation

The number and percentage of participants who ended product use early, as well as the reasons for terminating product use early, will be presented in a table overall and by site.

#### 6.1.4 Study Discontinuation

The number and percentage of participants who completed the study, as well as the reasons for non-completion, will be displayed in a table overall and by site.

# 6.1.5 Completion of Procedures

The completion of required and expected procedures will be displayed in a table overall and by site. The table will display the number and percentages of participant-visits for each procedure.

